#### CONFIDENTIAL

treatment arm at Day 14. The posterior probability that the true mean reduction from baseline for the Danirixin treatment group in sputum NETs is greater than a 0%, 15%, 30% and 40% reduction will be calculated, as appropriate, depending on the observed data.

Additionally, the mean and corresponding 95% credible interval for the difference between Danirixin and placebo at Day 14 will be produced. The posterior probability that the true relative reduction from baseline in sputum NETs is greater than a 0%, 15%, 30% and 40% reduction will be calculated, as appropriate, depending on the observed data.

The existing reference data may be used to construct the prior distribution for the placebo arm instead of a non-informative prior. A non-informative prior will be utilized for the other parameters in the statistical model as appropriate to their distribution.

Other efficacy data will be presented in tabular and/or graphical format and summarized descriptively. Full details of the analyses to be performed on all efficacy endpoints will be described in the reporting and analysis plan (RAP).

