2. SUMMARY OF KEY PROTOCOL INFORMATION

2.1. Changes to the Protocol Defined Statistical Analysis Plan

Protocol	Reporting & Analysis Plan	
Statistical Analysis Plan	Statistical Analysis Plan	Rationale for Changes

 Enrolled - All participants who sign informed consent 	
 Enrolled - All participants who sign informed consent and for whom a record exists on the study database 	
 Align with standard Enrolled population definition.

 Randomised 	
 mITT population defined to be used for selected displays 	
 Used for key displays

 Primary completer 	
 Population definition refined 	
 To allow for missing data and increase clarity

 Safety 	
 mITT population used for safety reporting 	
 Safety population not required.

 PK population 	
 PK population defined 	
 Used for PK displays

 Endpoint - Model specific PK parameters of danirixin (e.g., oral clearance, oral steady state volume of distribution). 	
 Danirixin concentration and standard pharmacokinetic (PK) parameters for danirixin (e.g. AUC, Cmax, tmax) 	
 Updated due to small number of participants with PK data

 Endpoints - serum IL-8 or sputum mucin 	
 Removed 	
 Not collected

 Primary analysis Bayesian 	
 Primary analysis Frequentist 	
 The primary analysis has been simplified as the historical data could not be used as a prior.

 Modified Primary Completer 	
 Population defined 	
 Defined to allow for a sensitivity around the definitions of quality for the samples

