2.3. Study Design

Overview of Study Design and Key Features	
<pre> graph LR A[30 days Screening period] --> B((R)) B --> C[Placebo, BD (~6 participants)] B --> D[Danirixin 35mg BD (~18 participants)] C --> E[14 days] D --> E E --> F[Early Withdrawal / Follow-up] </pre>	

*R=Randomization
 
Notes:
 
 • Early Withdrawal visit to occur as soon as possible (ASAP) after decision to withdraw by either investigator or participant • Follow up phone-call to occur within 7 days of last dose of study medication 	
Design Features	
 • Single centre, randomized, double-blind, sponsor open, placebo-controlled, 14-day mechanistic study evaluating the effect of danirixin in reducing NET formation.
Dosing	
 • Study treatment will be administered twice daily for 14 days.
Treatment Assignment	
 • Participants will be randomized (3:1) to receive either danirixin HBr 35mg or placebo. • GSK RandAll NG used to generate randomisation schedules.
Interim Analysis	
 • No formal interim analysis will be performed

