5. CONSIDERATIONS FOR DATA ANALYSES AND DATA HANDLING CONVENTIONS

5.1. Study Treatment & Sub-group Display Descriptors

Treatment Group Descriptions			
RandAll NG System		Data Displays for Reporting	
Code	Description	Description	Order in TLF
PBO	Placebo	Placebo	1
DNX	GSK1325756 (danirixin) 35mg HBr	DNX 35mg BD	2

Treatment comparisons will be displayed as follows using the descriptors as specified:

1. Danirixin vs. Placebo

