7. EFFICACY ANALYSES

7.1. Primary Efficacy Analyses

7.1.1. Endpoint / Variables

The primary endpoint will be the percent change (relative to baseline) in sputum NETs, quantified by Histone-elastase complexes, for danirixin.

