7.1.2. Summary Measure

Mean and 95% confidence interval will be calculated for the danirixin and placebo arms at day 7 and 14.

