7.1.5.1. Statistical Methodology Specification

Endpoint / Variables

 Sputum NETs quantified by Histone-elastase complexes
Model Specification

 The ratio of post-baseline NETs values to baseline NETS values will be log transformed prior to analysis. Note: $\log\left(\frac{NETs_{post}}{NETs_{baseline}}\right) = \log(NETs_{post}) - \log(NETs_{baseline})$. $y_{ij} = \beta_{baseline} \cdot \log(x_i) + \beta_{treatment} \cdot x_i + \beta_{day} \cdot x_{treatment} \cdot x_{ij} + \gamma_i + \epsilon_{ij}$ Where i is the index for each participant and j is the index for day
Model Checking & Diagnostics

 The mixed effect model will control for treatment, baseline, and day. An unstructured symmetric covariance structure will be used. Although if there are issues with convergence auto-regressive lag 1 can be used. It may be necessary to exclude placebo data from the analysis due to small cell size. The Kenward and Rodger method for approximating the denominator degrees of freedom and

correcting for bias in the estimated variance-covariance of the fixed effects will be used
 
 • If there are any departure from the distributional assumptions, alternative models will be explored using appropriate transformed data. Residual plots will be checked.
Model Results Presentation

 • Refer to Appendix 12 for detailed description of tables, figures, and listings

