12.12. Appendix 12: Example Mock Shells for Data Displays

Available Upon Request

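### The protocol plans a danirixin–placebo difference at Day 14; the visible SAP text names no such estimate and lets placebo be dropped from the primary model with no threshold

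*SAP*

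**What the plan says.** Protocol 10.3.1 first plans the danirixin-arm mean at Day 14 and then states: "Additionally, the mean and corresponding 95% credible interval for the difference between Danirixin and placebo at Day 14 will be produced". Posterior probabilities for the relative reduction follow.

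The SAP describes the primary analysis in these places:

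- **7.1.1, endpoint:** "The primary endpoint will be the percent change (relative to baseline) in sputum NETs, quantified by Histone-elastase complexes, for danirixin".
- **What is to be reported, in 7.1.2:** each arm on its own, with no difference or ratio between them: "Mean and 95% confidence interval will be calculated for the danirixin and placebo arms at day 7 and 14".
- **7.1.5.1, model:** a repeated-measures model on the log ratio to baseline with treatment, baseline and day. No contrast is named. The section also says: "It may be necessary to exclude placebo data from the analysis due to small cell size".
- **12.11.5 and 12.11.6:** Table 2.1 and Figure 2.1 are titled as adjusted change from baseline.
- **5.1:** "Treatment comparisons will be displayed as follows using the descriptors as specified", followed by one label, danirixin versus placebo, with no endpoint, day, scale or interval.
- **Appendix 12, table shells:** "Available Upon Request".
- **2.1, changes from the protocol:** the move from a Bayesian to a frequentist primary analysis, explained by "The primary analysis has been simplified as the historical data could not be used as a prior". Neither the between-arm difference nor the possible exclusion of placebo appears there.

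**The concern.** A within-arm change on danirixin mixes any drug effect with whatever else happens over 14 days, including drift and repeated sputum induction. Placebo is the only concurrent reference for these. The comparison is not fully randomised, because the Primary Completer population (SAP 4) requires acceptable sputum at Day 14, but it is the one the protocol planned.

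The exclusion clause puts that comparison at risk. Small cell size has no definition, and the design diagram in SAP 2.3 already shows about 6 on placebo, so the condition could be called met from the outset. A smaller cell was foreseeable: SAP 3.1 records 6 participants with poor-quality data and SAP 3.2 an early stop with 19 completers. Without a stated rule, the choice could be made with the arm results in view. Excluding placebo would also make the treatment term inestimable and leave the placebo mean and interval of SAP 7.1.2 without a model to produce them.

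A lesser point concerns baseline. SAP 5.2 and 12.6.3 let a screening sample replace a poor Day 1 sample. Entry requires more than 0.5 units/ml on the same assay, so those baselines may be high by selection. The documents do not say how many participants this affects.

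**Working it through.** **The plan's own figure.** Protocol 10.1 gives a 70% probability of being at least 50% certain that danirixin is below placebo. The prior SD reproduces: 0.3/1.645 = 0.182. With no sampling error the mixture prior gives 0.5 × 0.5 + 0.5 × Φ(0.3/0.182) = 72.5%, the ceiling. The step from 72.5% to 70% depends on the outcome variability, which the documents do not state. The 70% therefore cannot be checked, and the residual SD has to be assumed.

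**Assumed inputs.** Total log-SD 0.65 and baseline correlation 0.5 give a residual SD of 0.65 × √(1 − 0.25) = 0.56; the range taken is 0.4 to 0.8. The 18:6 split is planned. The others are assumed: 14:5 is 19 completers at about 3:1, and the three splits totalling 13 apply if all 6 poor-quality participants are among those 19.

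**Interval for the ratio.** For a danirixin and b placebo participants, the 95% factor is exp[t(a+b−3) × SD × √(1/a + 1/b)].

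| Split | t | √(1/a+1/b) | Factor, SD 0.56 | SD 0.4 to 0.8 |
|---|---|---|---|---|
| 18:6 | 2.080 | 0.471 | 1.73 | 1.48 to 2.19 |
| 14:5 | 2.120 | 0.521 | 1.86 | 1.56 to 2.42 |
| 10:3 | 2.228 | 0.658 | 2.27 | 1.80 to 3.23 |
| 11:2 | 2.228 | 0.769 | 2.61 | 1.98 to 3.94 |
| 12:1 | 2.228 | 1.041 | 3.66 | 2.53 to 6.39 |

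**How small the placebo cell could be.** If 6 of 19 completers are lost at random (hypergeometric), the chance that two or fewer placebo participants remain is 15% starting from 14:5 and 37% starting from 15:4.

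**Whether exclusion helps the danirixin mean.** Its factor is exp[t × SD/√a], with a+b−3 degrees of freedom if placebo stays and a−2 if it goes. At SD 0.56:

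- 18:6: 1.316 with placebo, 1.323 without
- 10:3: 1.484 with, 1.504 without
- 11:2: 1.457 with, 1.465 without

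With similar variances there is no gain.

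**When variances differ.** This was simulated as a Day 14 analysis of covariance with no drug effect, a single-visit approximation to the SAP model (10,000 trials per setting for the interval widths, 20,000 for coverage). If the placebo SD is 1.5 or 2 times danirixin's, exclusion narrows the danirixin interval: from 1.36 or 1.42 to 1.32 at 18:6, and from 1.52 or 1.59 to 1.48 at 10:3. Coverage of the ratio interval, across 18:6, 14:5, 10:3 and 11:2, is about 95% with equal SDs, 88 to 90% at 1.5 times and 79 to 85% at 2 times.

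**The case against.** The primary objective in both documents is the change from baseline on danirixin, and the protocol presents the difference as additional. SAP 7.1.1 therefore matches the objective, and what is missing is the second estimate. That is right, and nothing here claims more.

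SAP 5.1 signals that some comparison was intended, the model would yield one if placebo stays in, and the unseen shells may contain it. This limits the first half of the point to what the visible text specifies. It does not touch the exclusion clause, which would leave such a row empty.

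The clause says only that exclusion may be needed, and it concerns the model. Descriptive displays such as Tables 2.2 and 2.4 would still show placebo. This stands, but no visible text gives those displays a contrast, and they are unadjusted.

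The loss of the historical prior, which SAP 2.1 does disclose, helps explain why a placebo arm of about 6 became harder to use. It explains the change of method. A frequentist model can still estimate a difference, so the entry is incomplete.

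The study is estimation-only, but an estimate with an interval is all that is asked for.

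The strongest remaining point is about the remedy. If placebo is more variable, exclusion does sharpen the danirixin interval and the pooled-variance ratio under-covers. That is a reason to report the danirixin-only fit as well and to state the variance assumption.

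**Conclusion.** The point holds and should be fixed. The protocol plans a Day 14 danirixin–placebo difference, the visible SAP text does not name it, an open-ended clause allows the data it needs to be removed from the model, and SAP 2.1 records neither departure. This rests on the text alone and does not depend on the calculations. It does not show that the comparison was abandoned, because the shells are not in the document.

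The calculations add scale. The ratio would be known to within a factor of about 1.7 at the planned split and about 2.3 to 2.6 if two or three placebo participants remain, given a log-scale SD of 0.56 and the assumed splits. These intervals are imprecise but can be reported. Excluding placebo gains precision for danirixin only if placebo is the more variable arm.

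**What to change.** 1. **SAP 7.1.2, Table 2.1 and Figure 2.1:** add the Day 14 danirixin:placebo ratio of adjusted geometric mean changes with its 95% CI, from the model already specified, beside the per-arm changes. State that it is conditional on the Primary Completer population and assumes similar variances in the two arms.
2. **SAP 7.1.5.1:** delete the sentence allowing placebo to be excluded. If very few placebo participants remain, still report the interval and state its limits. Give any danirixin-only fit as a sensitivity analysis.
3. **SAP 2.1:** list any departure from protocol 10.3.1 that remains.
4. **Optional:** a sensitivity analysis restricted to Day 1 baselines.

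The cost is one model estimate, one table row, one row in SAP 2.1 and one deleted sentence; no new data are needed. The downside is a wide interval. At SD 0.56 an observed ratio of 0.70 would span 0.70/1.73 to 0.70 × 1.73, about 0.40 to 1.21, at 18:6. It would span about 0.31 to 1.59 at 10:3 and 0.27 to 1.83 at 11:2.

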7.2. Secondary Efficacy Analyses

7.2.1. Endpoint / Variables

The endpoint will be the change (relative to baseline) in sputum NETs, quantified by DNA-elastase and microscopy sputum resistin levels, ratio of sputum NETs to sputum neutrophils, sputum neutrophils, and sputum elastase activity. The mapping to dataset values are as follows. NETs quantified by microscopy are mean percent NETs per field. For a mapping of protocol variables to dataset variables (see [Dataset to Protocol Mapping](#))

7.2.2. Summary Measure

Unadjusted mean and standard error will be calculated for the danirixin and placebo arms at baseline, day 7 and 14. Unadjusted mean and standard error will be calculated for the percent change from baseline and absolute change from baseline for danirixin and placebo arms at day 7 and 14.

7.2.3. Population of Interest

Same as above, for NETs quantified by histone-elastase.

7.2.4. Statistical Analyses / Methods

Unadjusted means and standard errors will be calculated.

7.2.5. Endpoint / Variables

Change from baseline in peripheral blood neutrophil NET formation.

7.2.6. Summary Measure

Unadjusted mean and standard error will be calculated for the danirixin and placebo arms at baseline, day 7 and 14. Unadjusted mean and standard error will be calculated for the percent change from baseline danirixin and placebo arms at day 7 and 14

7.2.7. Population of Interest

The mITT population will be used.

7.2.8. Statistical Analyses / Methods

7.2.8.1. Statistical Methodology Specification

[figure not shown]
Unadjusted means and standard errors will be calculated.

7.3. Exploratory Efficacy Analyses

7.3.1. Endpoint / Variables

Exploratory endpoints include volatile organic compounds (VOC), ex-vivo neutrophil phagocytosis of bacteria by flow cytometry, and blood biomarkers. The blood biomarkers are plasma fibrinogen, serum C-reactive protein. Only VOCs from Cyranose, ex-vivo neutrophil phagocytosis and blood biomarkers will be part of SAC. No formal statistical analysis will be used to summarize the blood biomarkers, only unadjusted means. The urine will be stored for a two-year period, during which if there is a biomarker assay that comes forth that will support danirixin development program, analysis may be run.

The between tube, within day, and between day variability of the Cyranose device will be calculated using a multilevel multivariate model. Day will be the top level, followed by time of day, and tube. An unstructured covariance should be used to model the relationship between sensors, but the same covariance structure should be used across all tubes. Assume a constant variance between morning and afternoon and between days. Below is the model diagram for a single subject.

$$Y_{ijkl} = \mu + S_i + D_{i(j)} + T_{k(ij)} + \varepsilon_{ijkl}$$

In the case where the multilevel multivariate model does not converge then treat each sensor as independent and just run the multilevel model. If the multilevel models do not coverage, day and time of day can be collapsed into a single time level, in which we will only provide the variability of time rather than within day and between day.

Sputum microbiome, VOCs, and the relationship there in, will be investigated, but not included in the SAC due to the length of time needed to analysed the microbiome. The sputum microbiome will be analysed by Dundee. A secondary RAP to investigate VOCs and sputum microbiome will be written by the Computational Biology group to detail the analysis for this data. The results of this analysis will be written up in a report and added as an addendum to the CPSR.

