#### CONFIDENTIAL

Procedure	Pre-Screening and Screening 						Follow-up Phone call	Unscheduled visit 	Notes
	V0	V1	V2	V3	V 4	V5			
Dispense study medication			Х						
Monitor IP compliance (via manual counting and App)			Х	Х	Х			Digital App monitoring to begin at V2	
Collect IP					Х				

• The timing and number of planned study assessments, including safety, pharmacokinetic, pharmacodynamic/biomarker or other assessments may be altered during the course of the study based on newly available data (e.g., to obtain data closer to the time of peak plasma concentrations) to ensure appropriate monitoring.

- Any changes in the timing or addition of time points for any planned study assessments must be documented and approved by the relevant study team member and then
  archived in the sponsor and site study files, but will not constitute a protocol amendment. The IRB/IEC will be informed of any safety issues that require alteration of the safety
  monitoring scheme or amendment of the Informed consent form (ICF).
- Safety assessments should be performed in the following order where applicable/ possible: vital signs, ECG measurements, blood samples and spirometry.
  - Screening visit is split into pre-screening on visit 0 and screening on visit 1 although the visits may be performed on the same day. This is to a) enable participants to
    potentially have more than one attempt at sputum induction for meeting eligibility and b) to only collect minimal screening data for subjects who fail on the basis of the elevated
    NETs since that is the key inclusion criteria that may not be known from medical records.
  - 2. Unscheduled visits may be used to collect information related to adverse events, for follow up of any safety assessments, and also to complete assessments where participants were not able to perform these within the visit window for any reason. It is not necessary to carry out all of the assessments listed under an unscheduled visit at a single visit; the assessments performed should be driven by the need for the visit.
  - 3. VOC measurement should be undertaken prior to sputum induction at these visits.

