  - 4. Sputum induction (and associated VOC measurement and safety spirometry) at visit 1 is only necessary if participant unable to give sample at visit 0. Where the participant is judged by the investigator to have a borderline sputum NETs level (<0.5 units/ml) at visit 0, they will be invited to give a second sputum sample on visit 1 to re-assess eligibility.

  - 5. VOC measurements should be undertaken at the following timepoints at this visits: prior to sputum induction, and 4 hours post dose
  - 6. Hepatitis B (HBsAg) and Hepatitis C (HepC antibody) testing is required. If testing otherwise performed within 3 months prior to the first dose of study treatment, testing at screening is not required. Hepatitis C Ribonucleic acid (RNA) testing is optional; however a confirmatory negative Hepatitis C RNA test must be obtained, to be able to enroll participants with positive Hepatitis C antibody due to prior resolved disease.
  - 7. At visits 2 and 4, PK samples should be collected at the following time-points: pre-dose, 0.5, 1, 2 and 4 hours post-dose.
  - 8. At visit 3 only a pre-dose PK sample should be collected.
  - 9. Agreeing to genetic sample consent is not required for overall study participation. Informed consent for genetic sample must be obtained prior to taking sample.
  - 10. Pregnancy testing only required for women of child bearing potential (WOCBP). A positive urine pregnancy test requires confirmation with a serum pregnancy test.

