#### 9.1.3. Measurement of volatile organic compounds (VOCs)

Exhaled breath samples through normal tidal breathing will be collected via a ReCIVA (Owlstone Medical, Cambridge, UK) collection device, which connects a disposable face mask onto multiple sorbent tubes that bind VOCs. The sorbent tubes will be stored and later subject to analysis via one or more devices that measure patterns of exhaled VOCs, such as eNoses or Field asymmetric ion mobility spectrometry (FAIMS) devices, and may also be subject to gas chromatography mass spectrometry for comparison. Exhaled breath samples should be collected at the timepoints specified in the SoA, and samples should be collected prior to administration of bronchodilators and sputum induction (with the exception of the samples taken at 4 hours post dose). Further sampling considerations are detailed in the SRM.

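### The VOC variability model has no mean term for time point, so any systematic shift across the Visit 2 pair is reported as within-day variability of the device

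*SAP*

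**What the plan says.** SAP Section 7.3.1 states the aim: "The between tube, within day, and between day variability of the Cyranose device will be calculated using a multilevel multivariate model". The hierarchy is "Day will be the top level, followed by time of day, and tube". The equation, described as a diagram for a single subject, has an overall mean, a term S, a day term, a nested time-of-day term and an error. S is not defined. The one sentence that mentions morning and afternoon is "Assume a constant variance between morning and afternoon and between days". The two convergence fallbacks (treat sensors as independent; collapse day and time of day into one level) add no mean term for time. The covariates in SAP Section 5.3.1 (treatment and baseline) are tied to Sections 7.1 and 7.2, not to 7.3.

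The sampling times are in the Protocol's Schedule of Activities. For Visit 2, footnote 5 gives two: "prior to sputum induction, and 4 hours post dose". For the other visits with VOC sampling, footnote 3 gives one: "VOC measurement should be undertaken prior to sputum induction at these visits". Protocol Section 9.1.3 wants samples taken before bronchodilators and induction, "with the exception of the samples taken at 4 hours post dose". Under Protocol Section 6.3.1 participants arrive fasted and take danirixin with food. The result is displayed in SAP Table 2.22.

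**The concern.** The two Visit 2 samples are not repeats under like conditions. Bronchodilator, saline induction, food and the first dose of study treatment come between them, and the pre-induction sample is always first. If these steps move the VOC signal on average, the move is systematic. The model has nowhere to put a systematic move except the time-of-day variance, which Table 2.22 would show as within-day variability of the device. Anyone using that table to judge how repeatable the device is within a day would be reading a mixture of repeatability and procedure, food and dosing effects.

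**Working it through.** The plan gives no VOC variance, shift or precision target, so there is no figure of its own to reproduce. The check has three parts.

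**1. Which data inform the within-day component.** Visits 0, 3 and 4 have one scheduled VOC time each, as does Visit 1 when VOC is measured there. Visits 0 and 1 may fall on one day, but VOC at Visit 1 is conditional on the Visit 0 sputum result, and each sample would precede that visit's induction. So Visit 2 is the only scheduled within-day pair. The single-time days inform only the sum of the day and time-of-day variances; only Visit 2 separates them.

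**2. Algebra for an isolated pair.** Let σ_T² be the time-of-day variance, σ_e² the tube variance, m the tubes per time and d the mean shift. Then

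E[(post − pre)²]/2 − σ_e²/m = σ_T² + d²/2.

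With d = k·σ_T the relative overstatement is k²/2:

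- k = 0.5: 0.125, or +12.5%
- k = 1: 0.50, or +50%
- k = 2: 2.00, or +200%

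**3. REML on the study layout.** Layout: screening, Day 1 pre-induction, Day 1 at 4 hours, Day 7, Day 14. Assumed, because the documents give no values: one sensor, two tubes per time, S taken as a subject effect, and true variances subject 1, day 0.50, time of day 0.25, tube 0.25. Each setting had 150 runs. N = 19 is the number of completers in SAP Section 3.2; N = 24 is the planned number.

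Without a time-point mean, as in the SAP:

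| d in within-day SDs | Within-day, N=19 | Within-day, N=24 | Between-day, N=19 | Between-day, N=24 |
|---|---|---|---|---|
| 0 | 0.235 | 0.258 | 0.486 | 0.494 |
| 0.5 | 0.282 (+13%) | 0.286 (+14%) | 0.481 | 0.472 |
| 1 | 0.351 (+40%) | 0.385 (+54%) | 0.416 | 0.421 |
| 2 | 0.668 (+167%) | 0.645 (+158%) | 0.270 | 0.276 |

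Percentages are relative to the true 0.25. A repeat at N = 19 gave within-day 0.26, 0.28, 0.37 and 0.66 (+12%, +48% and +164% for the three non-zero shifts) and between-day 0.48, 0.47, 0.43 and 0.25. The tube component stayed at 0.25.

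At 2 SD the increase is below the algebraic +200%. The reason is in part 1: the single-time days hold the sum of day and time-of-day variance near 0.75, so REML restrains the within-day component and lowers the between-day one. At 2 SD the order reverses: 0.67 within day against 0.27 between days, when the truth is 0.25 against 0.50.

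With one fixed effect for 4 hours post-dose versus pre-induction, the within-day estimates for shifts 0, 0.5, 1 and 2 SD were 0.236, 0.258, 0.232 and 0.252 (N = 19) and 0.254, 0.254, 0.270 and 0.228 (N = 24). Between-day was 0.48 to 0.52 throughout.

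**The case against.** The strongest reply is that Section 7.3.1 is under-specified rather than wrong. S may be a sensor effect: day is called the top level and the equation is drawn for one subject. In that case each sensor has its own mean, and a claim that the model has a single common mean would go too far. The morning-and-afternoon sentence is only an equal-variance assumption and is compatible with different means. Both points stand, but neither reading of S supplies a mean term for time point, and the equation, its text and its fallbacks name none.

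A second reply concerns the target. The exploratory endpoint is variability of exhaled VOCs, and total within-day variability, including ordinary change over the day, is a legitimate description. That stands too, so a reader should not conclude that the exploratory question is answered wrongly. The difficulty is narrower: the SAP attributes the component to the device, and the only pair behind it straddles study procedures and dosing.

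A reader might also infer that treatment effects over visits are known to inflate the between-day component. The documents do not support this. Neither says danirixin is expected to change VOCs, and no size can be given. The effect shown here on that component runs the other way.

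Finally, the stakes are small. This is one descriptive table with no hypothesis test, individual VOC data appear in Listing 38, and other VOC analyses are left to separate plans. Saying that later VOC work would be misled is speculation.

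**Conclusion.** The point holds as a minor one. The model has no mean term for time point, and the one scheduled within-day pair is separated by bronchodilator, induction, food and first dose, so any systematic shift enters the within-day component. For shifts of 0.5, 1 and 2 within-day SDs the simulated overstatement is about 12–14%, 40–54% and 158–167%, with the between-day component pulled down from 0.50 to about 0.25–0.28 at the largest shift.

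The direction follows from the design. The size rests on the assumed shift and variances, none of which the documents give, and with no shift there is no bias. It would be a stronger reading to say that the reported variability is known to be distorted; nothing in the documents establishes that a shift exists. The primary analysis is not affected.

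**What to change.** Add one fixed effect per sensor for Visit 2 samples at 4 hours post-dose versus pre-induction, and keep day, time of day and tube as variance levels. It must be estimated by pooling subjects: with one pair per subject, a single-subject fit cannot separate shift from within-day variance. Define S. Report the estimated shift beside the variance components in Table 2.22.

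If the model converges, add a time-point by treatment term, or give a placebo-only sensitivity estimate, since the first dose falls inside the pair. The common effect does most of the work. If the shift differs between arms by δ, 3:1 allocation leaves (3/4 × 1/4)·δ²/2 ≈ 0.094δ² in the within-day variance of an isolated pair, or about 9% when δ is one within-day SD. A placebo-only estimate would be imprecise: 19 completers split 3:1 give about 19/4 ≈ 5 on placebo. Visit and treatment by visit terms are optional, as data permit.

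The cost is a few parameters per sensor and some added convergence risk at this sample size, for which the SAP's fallback to independent sensors already provides. No new data are needed. Variation between people in their response to induction, food or dosing would still sit in the within-day component, and a table footnote should say so.
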